IRB/ERB	Institutional Review Board/Ethical Review Board: a board or committee (institutional, regional, or national) composed of medical, professional and non-medical members whose responsibility it is to verify that the safety, welfare, and human rights of the subjects participating in a clinical trial are protected.
irRC	Immune-Related Response Criteria
ITT	Intention to Treat
IV	Intravenous, usually referring to a medication or substance given into a vein.
LDH	Lactate Dehydrogenase
LFT	Liver Function Test
mAB, mAb	Monoclonal Antibody
MDSC	Myeloid-Derived Suppressor Cells
mg	milligram: 1/100 of a gram
m²	meters squared
NCA	Non-Compartmental Analysis
NCCN	National Comprehensive Cancer Network
NSCLC	Non-Small Cell Lung Cancer
OS	Overall Survival
Patient	A subject with a defined disease
PBMC	Peripheral Blood Mononuclear Cells
PFS	Progression Free Survival
PD	Progressive Disease
PET	Positron Emission Tomography
PK	Pharmacokinetic
PPK	Population Pharmacokinetics
PR	Partial Response
RECIST	Response Evaluation Criteria in Solid Tumor
RT	Radiation Therapy/Radiotherapy
SAE	Serious Adverse Event
SD	Stable Disease
TAA	Tumor Associated Antigens
TIL	Tumor Infiltrating Lymphocytes
TNM Staging	Tumor, Node and Metastasis Staging
Treg	Regulatory T Cells
Wt	Weight

STUDY SCHEMA

STUDY DESIGN

This is a 30 patient single arm, open label, phase 2 trial adding neoadjuvant and adjuvant pembrolizumab to surgery and standard post-operative therapy in early stage non-small cell lung cancer. Patients with clinical stage IB (> 3cm), II, or IIIA (N0-2) NSCLC and no prior therapy for their current diagnosis of lung cancer will be eligible for the study. Patients will receive two cycles of neoadjuvant pembrolizumab. Patients will undergo standard surgical resection of their lung cancer as deemed appropriate by their surgeon, followed by standard adjuvant chemotherapy (+/- radiation therapy) for their lung cancer as deemed appropriate by their medical oncologist. Patients will receive 4 cycles of adjuvant pembrolizumab after the completion of all standard therapy. Follow-up after completion of therapy will be per institutional standard practice.

PATIENT ELIGIBILITY

- All patients must have histologically documented clinical stage IB (\geq 3cm), IIA/IIB, or IIIA (N0-2) NSCLC.
- **NO** prior chemotherapy, radiation therapy or biologic/targeted therapy for current diagnosis NSCLC.
- ECOG Performance Status of 0-1

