- No active invasive malignancy in the past 2 years other than non-melanoma skin cancer. Cancers that are in-situ are not considered invasive.
- Patient has provided informed consent and has signed Informed Consent Form.
- No autoimmune disease that would constitute contraindication to receive pembrolizumab.

REQUIRED LABORATORY DATA

- Hemoglobin \geq 9 g/dL or \geq 5.6 mmol/L without transfusion
ANC/AGC \geq 1500/ μ L
- Platelets \geq 100,000/ μ L
- Creatinine \leq 1.5 X ULN or creatinine clearance \geq 60 ml/min
- AST/ALT \leq 2.5x ULN
- Bilirubin \leq 2.0 x institutional ULN
- INR or PT \leq 1.5 x ULN unless on anticoagulants
aPTT \leq 1.5 x ULN unless on anticoagulants

Neoadjuvant Treatment:

Pembrolizumab: 200 mg IV over 30 minutes on days 1 & 22 (every 21 days x 2 cycles)

Surgery: Standard surgical evaluation to occur day 29 to day 56 (at least 2 days after second dose of Pembrolizumab)

Adjuvant Treatment:

Chemotherapy: Standard adjuvant chemotherapy as per treating medical oncologist.

Radiation: Standard adjuvant post-operative radiation therapy in selected patients for standard clinical indications such as N2 node metastases and /or close/positive tumor surgical margin.

Pembrolizumab: 200 mg IV over 30 minutes every 21 days times 4 cycles

- Patients who receive both adj CT plus Adj RT should start Pembrolizumab within 8 months of surgery.
- Patients who receive only one modality of adj therapy (e.g. CT alone or RT alone) should start Pembrolizumab within 6 months of surgery
- Patients who do not receive any additional therapy should start Pembrolizumab within 4 months of surgery.

Correlative Science Measures: (refer to Appendix B for further details on the correlative science outcomes.)

- 1) Tumor samples will be analyzed for tumor infiltrating T cells with specificities against tumor associated antigens. Tumor samples will also be evaluated to monitor populations of infiltrating regulatory T cells, myeloid-derived suppressor cells (MDSC), as well as activated and exhausted T cells.
- 2) Blood samples will be analyzed for circulating T cells with specificities against tumor associated antigens: prior to treatment, before surgery, after surgery, and after completion of adjuvant pembrolizumab. Blood samples will also be analyzed to monitor circulating populations of regulatory T cells, myeloid-derived suppressor cells (MDSC), as well as activated and exhausted T cells.

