7) The proportion of patients with detectable circulating T cells specific against TAA after the protocol treatment will be estimated and its confidence interval will be provided. An exact binominal test will be used to test the increase in the proportion of patients with detectable circulating T cells specific against TAA after the protocol treatment relative to baseline.

8) Estimate the rate of pathologic response rate for neoadjuvant pembrolizumab in early stage NSCLC. The pathologic response rate along with its 95% exact confidence interval will be estimated.

9) Determine if the immunomodulatory effects of neoadjuvant chemotherapy plus pembrolizumab impact the suppressive mechanisms, restoring functional reactivity to important anti-tumor effector cell populations. Functional TAA-specific T cell reactivities will be measured in the blood at 4 time points: baseline, after second dose pembrolizumab, after surgery, and after completion adjuvant pembrolizumab. A Wilcoxon rank sum test will be used to test for differences from baseline, as well as for any association between each reactivity measure and pathologic response to neoadjuvant therapy.

10) Explore an alternative definition for detectability suitable for expression values generated using Boolean gating, and determine the percentage of patients with circulating T cells meeting this definition. The percentage of patients with circulating T cells meeting the new definition of detectable and its 95% exact confidence interval.

11) Perform gene expression analysis on tumor to elucidate genes associated with function and modulation of the PD-1/PD-L1 axis.

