10.0 Sample Procurement and Handling

10.1 Blood Specimens

Blood will be collected 4 times to assess longitudinal analyses of T cell and MDSC phenotypes and other blood based biomarkers.

Samples will be collected to detect activated CD8+ T cells with specificity against tumor antigens and CD4 and CD8 functional memory. At each blood collection, 4 tubes of 8.5-ml each will be collected. The tubes used will be ACD anti-coagulated Vacutainer (yellow tops). The following time points will have blood collections

(Outside Sites see appendix G for processing/shipping):

Collection 1: Baseline prior to treatment initiation

Collection 2: After dose # 2 pembrolizumab and prior to surgery

Collection 3: Two to six weeks after surgery prior to initiation of adjuvant chemotherapy.

Collection 4: Three to six weeks after last dose of adjuvant pembrolizumab

**** Note: it is imperative tube is filled to the fill line for proper additive to blood ratio. Specimen is not evaluable if not filled to the fill line. If unable to obtain the 4 required tubes, fill as many tubes as possible to the fill line.

*****If EOS (End of Study) occurs and no adjuvant treatment with Pembrolizumab has occurred, draw Collection #4 at End of Study visit.

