- 1) Whether the cumulative percentage of deaths among all treated patients related to any of the study treatments from the first pembrolizumab treatment until 30 days after surgery exceeds 17%.
- 2) If the cumulative percentage of all treated patients deemed unable to go to surgery due to adverse events attributed to neoadjuvant therapy exceeds 20%. The percentage of patients unable to go to surgery after pembrolizumab is a conservative estimate based on data reported for a SWOG trial that studied neoadjuvant chemotherapy in early stage lung cancer (22).

The first 10 treated patients will be evaluated for safety and feasibility. If in the first ten patients the criteria for overall therapy being not safe or feasible is met, accrual to the study will be suspended to allow for investigation. After consideration by the study team and the IRB, a decision will be made as to whether accrual can be resumed, potentially with modifications to entry criteria and/or study conduct. In addition, all toxicity patterns will be monitored by the DCI Safety Oversight Committee.

The trial will be stopped for accrual whenever a total of 35 patients are registered or at least one of the thresholds of the safety and feasibility criteria is exceeded. In the event either of these two thresholds is exceeded, the investigational therapy will be considered “infeasible” in this setting.

Accrual and follow-up

With an expected rate of 2 patients being enrolled each month, the trial will take about 16 months to reach the target accrual. All registered patients will be followed for tumor response, disease free survival and overall survival.

Statistical Analysis Plan

Surgery feasibility rate, the primary endpoint of the trial, will be analyzed using the data from all evaluable patients, who are defined as the patients who meet eligibility criteria and has received at least 1 dose of pembrolizumab. The surgery feasibility rate of neoadjuvant pembrolizumab as well as its confidence interval will be estimated.

Secondary Objectives

All secondary objectives are considered exploratory in nature, and type I error will not be controlled for multiplicity. P-values for these statistical tests will be provided for descriptive purposes. However, if a statistical test on a secondary outcome is significant at the 2-sided significance level of 0.01, the finding will be considered worthy of future investigation.

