- 9) Determine if the immunomodulatory effects of neoadjuvant chemotherapy plus pembrolizumab impact the suppressive mechanisms, restoring functional reactivity to important anti-tumor effector cell populations. Functional TAA-specific T cell reactivity’s will be measured in the blood at 4 time points: Collection 1, 2, 3 and 4. A Wilcoxon rank sum test will be used to test for differences from baseline, as well as for any association between each reactivity measure and pathologic response to neoadjuvant therapy.
- 10) Explore an alternative definition for detectability suitable for expression values generated using Boolean gating, and determine the percentage of patients with circulating T cells meeting this definition. The percentage of patients with circulating T cells meeting the new definition of detectable and its 95% exact confidence interval.
- 11) Perform gene expression analysis on tumor to elucidate genes associated with function and modulation of the PD-1/PD-L1 axis.

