29.2 Appendix B- Correlative Science Measures

Correlative Science Primary Objective

Circulating T Lymphocytes with Specificity Against Tumor Associated Antigens:

Detectable circulating T cells with specificity against TAA will be identified using the following process:

Whenever individual patient tumor tissue is available for analysis, the expression of 10 highly conserved TAA's (see Table I below) will be assessed using standard Real-Time (RT) PCR technology. Peptide pools representing the three most highly expressed TAA's by each tumor will serve as antigen-specific stimulators for PBMC isolated from the same patient at the 4 specified time points. If no tumor tissue is available for TAA expression analysis, peptide pools representing the three most commonly expressed TAA's on NSCLC, namely Survivin, PRAME, and MAGE-A3, will be chosen as antigen-specific stimulators.

The percentage of CD4, CD8, and double positive (DP=CD4+/CD8+) lymphocytes with specificity against the three selected TAA's, will be calculated for each of 4 individual functional markers (IL-2, TNF- α , IFN- γ , and CD107 underlined below). For each peripheral blood collection, the lab will generate a total of 12 lymphocyte values (4 values each for CD4, CD8 and DP) for each of the three TAA's and for CD3/CD28 (used as a positive control), as well as generating 12 background unstimulated negative control values. All values will be expressed as percentages. A patient will be considered to have detectable circulating T cells if ≥ 1 of the 36 percentage values (12 values * 3 TAA's) satisfies the definition of "detectable" as described in section 26.0 (a lymphocyte percentage of $\geq 0.05\%$ at the pre-surgical peripheral blood collection (Collection 3) with each value also being at least twice that of the background unstimulated negative control value).

Table I **TAA Peptide Pools**
(15-mers, overlapping by 11 amino acids)

Survivin (33 peptides)
PRAME/OIP4 (125 peptides)
MAGE-A3 (76 peptides)
Melan A/MART-1 (27 peptides)
Gp100 (163 peptides)
Tyrosinase (117 peptides)
NY-ESO-1 (43 peptides)
MAGE-A1 (75 peptides)
MAGE-A4 (77 peptides)
CEA (173 peptides)

Assessing detectable circulating T cells specific against three TAA's (individually selected from the Table I list of TAA's using the process outlined above) in the following combinations of T cells and functional markers:

- * %**CD4**+/**CD69**+/**IL-2**+
- *%**CD4**+/**CD69**+/**TNF- α** +
- *%**CD4**+/**CD69**+/**IFN- γ** +

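### Change from baseline in T-cell reactivity is tested with an unpaired rank-sum test on paired samples, and Appendix B ties the 'detectable' endpoint to a pre-surgical Collection 3 that is drawn after surgery

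*Combined protocol and SAP*

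**What the plan says.** **Test.** Section 27.1, secondary objective 9, reads: "A Wilcoxon rank sum test will be used to test for differences from baseline". The same sentence goes on to use that test for association with pathologic response. Sections 1.3, 4.2 (item 9) and 5.1.1 repeat it. Section 4.2 lists the time points as "baseline, after second dose pembrolizumab, after surgery, and after completion adjuvant pembrolizumab". The Study Schema describes the design thus: "This is a 30 patient single arm, open label, phase 2 trial". Appendix B confirms that the blood cells tested at the four time points come from the same patient. A secondary result that is "significant at the 2-sided significance level of 0.01, the finding will be considered worthy of future investigation".

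**Time point.** Under its correlative primary objective, Appendix B applies the detectability threshold "at the pre-surgical peripheral blood collection (Collection 3"), and refers to Section 26.0 for the definition. Section 10.1 schedules the draws differently: "Collection 2: After dose # 2 pembrolizumab and prior to surgery" and "Collection 3: Two to six weeks after surgery prior to initiation of adjuvant chemotherapy". Secondary objective 7 estimates the proportion of patients with detectable circulating T cells after study treatment and compares it with baseline, without naming a collection.

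**The concern.** The rank-sum test compares two separate groups. Here each later value has a partner, the same patient's baseline, and the test discards that link. It suits the second use in the sentence, responders against non-responders, but not the first. At stake is whether a real immunologic change passes the 0.01 screen by which the plan picks findings to pursue.

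The second defect concerns what is measured. A draw before resection and a draw two to six weeks after it are different measurements. Two analysts following the documents could report different proportions from the same data.

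**Working it through.** The plan gives no power, effect size or correlation for objective 9, so there is no stated figure to reproduce.

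**Inputs from the documents**
- Two-sided level 0.01 (Section 27.1).
- 30 evaluable patients (Section 27.1).
- Surgery rates of 0.80 and 0.65 in the primary hypotheses. These give 30 × 0.80 = 24 pairs and 30 × 0.65 = 19.5, taken as 20, for draws that require surgery.
- Baseline against Collection 2, drawn before surgery, could have up to 30 pairs.

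**Assumptions**
- Within-patient correlation ρ of 0, 0.3, 0.5 or 0.7.
- A shift of 0.5 SD.
- Bivariate normal values with unit SD.

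**Why pairing matters.** The variance of a within-patient difference is 2σ²(1 − ρ). The unpaired test in effect works with 2σ². In SDs of the difference, a shift δ (in σ units) becomes δ / √(2(1 − ρ)). For δ = 0.5:
- ρ = 0: 0.5/√2.0 = 0.35
- ρ = 0.3: 0.5/√1.4 = 0.42
- ρ = 0.5: 0.5/√1.0 = 0.50
- ρ = 0.7: 0.5/√0.6 = 0.65

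The paired test gains from this as ρ rises; the rank-sum test does not.

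**Power at two-sided 0.01, rank-sum / signed-rank** (20,000 simulated datasets per cell; rank-sum by normal approximation, signed-rank by its exact null distribution)

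| Pairs | ρ = 0 | ρ = 0.3 | ρ = 0.5 | ρ = 0.7 |
|---|---|---|---|---|
| 20 | 13% / 13% | 9% / 18% | 7% / 29% | 4% / 50% |
| 24 | 16% / 16% | 13% / 24% | 10% / 36% | 6% / 61% |
| 30 | 22% / 22% | 19% / 33% | 16% / 49% | 11% / 76% |

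**Actual size of the nominal 1% test, 24 pairs.** Rank-sum: 0.8% at ρ = 0, 0.2% at 0.3, and below 0.1% at 0.5 and above. Signed-rank: 0.9% to 1.0% throughout.

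**Sensitivity**
- Log-normal values, 24 pairs, ρ in the same order: 16% / 14%, 13% / 20%, 9% / 30%, 7% / 52%.
- A larger shift of 0.8 SD, 24 pairs, ρ = 0.5, with a slightly conservative approximation for the signed-rank test: 50% / 82%.

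**Where Collection 3 falls**

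| Place | Timing |
|---|---|
| Appendix B | Pre-surgical |
| Section 9.6 | 2–6 weeks after surgery |
| Section 10.1 | 2–6 weeks after surgery |
| Appendix A, footnote j | 2–6 weeks after surgery |
| Appendix A, footnote R | 2–6 weeks after surgery |
| Appendix F | 2–6 weeks after surgery |
| Appendix G | 2–6 weeks after surgery |

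The Study Schema gives the same order, "prior to treatment, before surgery, after surgery, and after completion of adjuvant pembrolizumab", so the third draw is post-surgical there too. The post-dose draw before surgery is Collection 2. Section 26.0 contains no definition of detectability. The 0.05% rule stands in Sections 1.4, 4.2 (item 4), 5.1.2 and 27.1 (item 4), where it is stated for tumor-infiltrating lymphocytes. Objective 7 does not settle the matter: its wording could also mean Collection 4, after adjuvant pembrolizumab.

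**The case against.** **It may be a naming slip.** For its exploratory outcome 4, Appendix B plans to analyze changes across time points, show them in a boxplot and report the median change by pathologic response. Pairing is therefore probably intended. But that text names no test, and the four places that do name one name the unpaired test. Followed literally, the plan discards the pairing.

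**The power figures are soft.** This stands as a caution on size.
- The shift is as much an assumption as the correlation. At 1.0 SD (24 pairs, ρ = 0.5) the gap is 80% against 96%.
- If many values sit at a detection floor, ties shrink the gap. With about 69% of baseline values floored, which is also an assumption, power is 7% against 14% at ρ = 0.5 and 5% against 22% at ρ = 0.7. At ρ = 0 the rank-sum test does better, 12% against 8%.
- A rank-sum test could use all 30 baselines against 24 later values. That raises its power from 10% to 13% at ρ = 0.5 and from 6% to 10% at ρ = 0.7.

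In none of these cases does the direction reverse at the positive correlations examined.

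**The consequence is modest.** All secondary objectives are exploratory and their p-values descriptive. Sections 4.2 and 27.1 list the circulating T-cell endpoint as a secondary objective, despite Appendix B's heading. The sampling schedule is consistent, so sites should not draw blood at the wrong time; only the endpoint definition is unclear. All of this is right. It limits the weight of the point but does not remove either defect.

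**Conclusion.** Both parts hold. The test named for change from baseline does not fit the data. With positive within-patient correlation it is conservative and loses power: under the 0.5 SD normal model with 24 pairs, the shortfall runs from nil at ρ = 0 to 55 percentage points at ρ = 0.7 (61% − 6%). The amount depends on the assumed correlation, shift and distribution; the mismatch between test and design does not. The timing of the detectability endpoint is contradictory within the current text, and its cross-reference leads to a section without a definition. The textual findings are firm. The point is worth correcting before analysis, but the primary endpoint and its conclusion are unaffected.

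**What to change.** 1. In Sections 1.3, 4.2 (item 9), 5.1.1 and 27.1 (item 9), name the Wilcoxon signed-rank test, or another paired method, for differences from baseline. Keep the rank-sum test for pathologic responders against non-responders.
2. Reconcile Appendix B with Section 10.1 by naming one collection for the detectability endpoint, and name the same one in objective 7. The word pre-surgical points to Collection 2, but the sponsor must confirm the intended draw. State that the same threshold applies to the baseline sample, since objective 7 compares against it.
3. Replace Appendix B's reference to Section 26.0 with one to the place where the definition stands.

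The cost is wording in four sections and Appendix B, with the matching entry in objective 7, and one line of programming. No new samples, visits or patients are needed.

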29.0 LIST OF APPENDICES

- Appendix A Study Schedule
- Appendix B Correlative Science Measures
- Appendix C Performance Status Criteria
- Appendix D Standard Cockcroft and Gault Formula for Calculated Creatinine Clearance
- Appendix E Site Biospecimen Processing Flow Chart
- Appendix F Biomarker Blood Specimens for Correlative Sciences-Duke processing
- Appendix G Biomarker Blood Specimens for Correlative Sciences- Processing and Shipping for Outside Sites
- Appendix H Surgical Tissue Specimen for Correlative Sciences-Duke Processing
- Appendix I Surgical Specimen Tissue Handling & Processing for Shipping- Outside Sites

29.1 Appendix A: STUDY SCHEDULE

Examination	Baseline (screen) ^a	Neoadjuvant RX		Evaluation post pembro ^k	Surgery ^p	Post Surgery FU ^r
		Cycle1	Cycle 2			
Day	30 to 0	1 (+/- 3 days)	22 (+/- 3 days)	pre-surgery	29 – 56 (from C1D1)	2-6 wks. post Surgery
Informed Consent	X					
Eligibility	X					
Medical Hx/Demo/ Smoking Hx	X					
Height	X					
Vital Signs (temp, RR, B/P, pulse)	X	X	X	X		X
Weight/BSA	X	X	X	X		X
Physical Exam	X	X	X	X		X
Performance Status	X	X	X	X		X
Hematology ^{b,c,e}	X	X	X	X		X
Chemistries ^{b,d,e}	X	X	X	X		X
Serum Beta HCG ^h	X	X ^h				
Calculated Creatinine ^{e,f} Clearance	X					
Thyroid Functions (T3, FT4, TSH) ^e	X			X		
PT(INR), aPTT ^e	X					
Urinalysis	X					
PFTs (FEV1/DLCO) ^e	X					
Radiologic Eval ^g	X			X ^g		X ^g
Medical & Surgical Evaluation	X			X		
EKG	X					
Tumor Histology	X					
Adverse Events		X	X	X		X
Concomitant Meds	X	X	X	X		X

Pembrolizumab		X	X			
Blood Sampling ^j	X ^j			X ^j		X ^j
Surgical Specimen ^p					X	
Tumor Biopsy Slides ⁿ					X	
Examination	STD ADJ CT/RT ^l	Adjuvant Pembrolizumab ^m				EOS ^s Follow-Up
		Cycle 1 ^m	Cycle 2	Cycle 3	Cycle 4	
Day		1	22	43	64	≥30 d post Pembro ^j
Informed Consent						
Eligibility						
Medical History/Demo- Graphics/Smoking Hx						
Height						
Vital Signs (temp, RR, B/P, pulse)		X	X	X	X	X
Weight/BSA		X	X	X	X	X
Physical Exam		X	X	X	X	X
Performance Status		X	X	X	X	X
Hematology ^{b,c,e}		X	X	X	X	X
Chemistries ^{b,d,e}		X	X	X	X	X
Serum Beta HCG ^h		X	X	X	X	
Thyroid Functions (T3, FT4, TSH) ^e		X		X		X
PT(INR), aPTT ^e						
Urinalysis						
PFTs (FEV1/DLCO) ^e						
Radiologic Evaluation ^g						
Med/surg Evaluation						
EKG						

Tumor Histology						
Adverse Events		X	X	X	X	X
Concomitant Meds		X	X	X	X	X
Pembrolizumab		X	X	X	X	
Blood Sampling ^j						X ^j
Surgical Specimen ^p						
Tumor Biopsy Slides ⁿ						

To allow for patient and investigator schedules, holidays, weather or other emergencies requiring facilities to be closed, visits can be performed ±3 days of scheduled visit

a Pre-enrollment baseline (screen) assessments are to be performed within -30 to 0 days unless otherwise specified.

b May be obtained within 3 days of pembrolizumab dosing

c Hematology values to include Hgb/Hct, WBC with auto or manual differential, platelets

d Chemistries to include Na⁺, K⁺, Cl⁻, total protein, albumin, calcium, glucose, BUN, creatinine, total bilirubin (direct bilirubin if total is elevated above upper limit of normal), alkaline phosphatase, SGOT, SGPT, LDH, uric acid, magnesium, phosphorus. **e** Baseline required labs to be performed within 30 days of enrollment Pre-study tests may be used for day 1, cycle 1 tests if obtained within 14 days of day 1 cycle 1 treatment. PFT's per institutional standards.

f Calculated creatinine clearance (see appendix D)

g Radiologic evaluation: pre-treatment clinical staging PET/CT of chest/abdomen, brain MRI or CT as per standard of care (these may be performed up to 42 days); after completing cycle#2 Pembrolizumab therapy (prior to surgery) chest CT; post- surgery recommend chest CT every 3-4 months (or per institutional standard of care) for 2 years

h All WOCBP MUST test negative for pregnancy within 48 hours prior to any initial study procedure based on a serum pregnancy test. If subject uses appropriate contraceptive methods (section 6.2) from the time of the initial serum pregnancy test, then the subsequent pregnancy test can be done within 72 hours before receiving pembrolizumab. If appropriate contraceptive methods are not begun immediately with the first serum pregnancy test, then subsequent serum pregnancy tests must be done within 48 hours prior to the study drug administration. If the pregnancy test is positive, the subject must not receive pembrolizumab and must not be enrolled in the study, or will be removed from treatment.

j Blood samples to assess activated CD8+ T cells with specificity against tumor antigens and CD4 and CD8 functional memory. **Collection 1:** Baseline: pre-dose #1 pembrolizumab. **Collection 2:** After second dose of Pembrolizumab (cycle 2) and prior to surgery. **Collection 3:** 2-6 weeks after surgery. **Collection #4:** Three to 6 weeks after last dose of adjuvant pembrolizumab. 4 tubes of 8.5 ml each (ACD anti-coagulated Vacutainer yellow tops).

k Evaluation Post pembrolizumab prior to surgery. Final visit (if \leq grade 1 toxicity) for those subjects that come off treatment early for progression of disease, intolerance to protocol therapy, for other reasons, or patient withdraws consent; safety evaluation should occur 30 days (+/- 5days) after last dose pembrolizumab or before initiation of a new anti-neoplastic cancer treatment (whichever comes first).

L Post-op standard therapy, including adjuvant CT and RT, based on final pathologic stage of cancer, tumor margins, and other standard clinical criteria. Post-op therapy is non-study specific and can be given through the primary oncology team.

m Adjuvant Pembrolizumab: Patients who receive both adj CT plus adj RT should start Pembrolizumab within 8 months of surgery. Patients who receive only one modality of adj therapy (e.g. CT alone or RT alone) should start Pembrolizumab within 6 months of surgery. Patients who do not receive any adjuvant therapy should start Pembrolizumab within 4 months of surgery.

n Tumor Biopsy Slides (appendix I)

P Surgery to occur at 4-8 weeks (29-56 days). If dose # 2 pembrolizumab delayed, there is to be at least 2 days between this infusion and surgery. Tumor Specimen collection (appendices G & H)

R Post-Surgery F/U visit: Two to 6 weeks following surgery. Subjects with bulky residual adenopathy such that resection was not attempted will be removed from protocol therapy and should receive standard oncology care as deemed appropriate by the treating physician. Subjects with positive surgical margins or N2 disease will be removed from protocol and considered for standard of care post-operative radiation +/- standard chemotherapy as deemed appropriate by their physician. Subjects who are completely resected or who refuse or cannot receive adjuvant chemotherapy will be given the option of receiving adjuvant Pembrolizumab. Collection #3 research blood sample 2-6 weeks after surgery prior to initiation of adjuvant CT.

S End of Study Visit: End of study evaluation is to occur approximately 30 days or more after adjuvant Pembrolizumab treatment. SAEs will be collected for 90 days after the end of treatment. Final research blood sample will be collected (collection #4). Chest CT if applicable (per radiologic evaluation, Appendix A)

T Follow-Up: Patients should have follow-up every 3-4 months as per standard care (of the treating institution (recurrence and survival) for 2 years unless patients has experienced > grade 1 toxicity related to Pembrolizumab (in which case follow until resolution of the AE to Grade 0-1, patient deemed stable by investigator, or new anti-neoplastic therapy has begun.). After 2 years follow every 6 months for up to five years. These evaluations may be coordinated with visits for radiologic disease evaluation or occur via phone follow-up. Lab assessments will be at the discretion of treating physician.

* Upon lung cancer relapse, radiologic imaging of sites of failure is at the discretion of the treating physician.

